5. STATISTICAL CONSIDERATIONS

5.1. Study Design for Randomized Study

The randomized study will test two interventions – the ETRIC consent form vs. the standard consent form for patients participating in the BMT CTN 1101 and 1301 studies. The BMT CTN 0901 trial and BMT CTN 1203 trial were removed as parent protocols for the BMT CTN 1205 study due to their closure to accrual on April 18, 2014 and May 13, 2016, respectively. Those who enrolled in the BMT CTN 1205 prior to the BMT CTN 0901 and BMT CTN 1203 closures will be included in the analysis.

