5.5. Analysis Plan

The primary analysis will be performed using the intention-to-treat principle so that all randomized patients will be included in the analysis. The t-test or the Mann-Whitney test will be used if the t-test assumptions are violated. Secondary endpoints of subjective comprehension, anxiety, satisfaction, and information location will be analyzed with the Mann-Whitney test. The binary outcome of consent rates will be compared using the Fisher exact test. The above unadjusted analyses will be complemented by analyses that adjust for potentially confounding

variables in regression analyses. Generalized estimating equations (GEE)⁵⁰ will be used to control for effect of confounding variables (e.g., patient demographics, health literacy level, strata) and a potential consenter effect (as more than one clinician could be involved in the consent process at a clinical trial site). GEE with identity link will be used for comprehension, anxiety and satisfaction analyses. Information location will be analyzed with LOG link and LOGIT link with accrual outcome. Variance will be estimated with the sandwich estimator if the number of consenters is > 30; otherwise the “leave-one-consenter-out” jackknife variance estimation will be used.⁵¹ Exact logistic regression will be used with accrual if the problem of small counts appears. Otherwise Wald tests will be used for significance testing. All two-way interactions between the group indicator (ETRIC vs. standard) and confounding variables will be tested and added to the model if significant. It is expected that all confounders will be analyzed as fixed effects except for the consenter which will be the repeated factor in the GEE. The form of continuous predictors will be either linear, quadratic, or categorized depending on the number of clusters observed in the dataset. Every category in categorical variables will have at least 10 subjects otherwise we will consider merging with neighboring categories. The presence of missing data in excess of 10% will be addressed by developing an imputation model for missing components given the observed part. Then, the multiple imputations approach will be used to estimate regression parameters and their standard errors.⁵²

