BMT CTN #1205 Statistical Analysis Plan (SAP)

Drafted by: [name] on 9/17/16

PROTOCOL: Easy-to-Read Informed Consent (ETRIC) for Hematopoietic Cell Transplantation Clinical Trials

Protocol Synopsis:

The BMT CTN protocol #1205 titled “Easy-to-Read Informed Consent (ETRIC) for Hematopoietic Cell Transplantation Clinical Trials” is a randomized, multicenter, prospective comparative study of ETRIC or standard consent form to improve patient comprehension of BMT CTN parent clinical trials. The primary objective is to compare objective comprehension scores on the Quality of Informed Consent (part A) instrument between patients randomized to the ETRIC versus the standard consent arms. Secondary objectives are to compare the following measures between the two arms: (1) subjective comprehension scores on the Quality of Informed Consent (part B) instrument and the modified Deaconess Informed Consent Comprehension Test instrument, (2) state anxiety scores on State Trait Anxiety Inventory instrument, (3) satisfaction score, (4) time taken for information location, and (5) patient consent rates on parent clinical trials. Per the original study design, the target sample size was 160 patients with 80 on each arm ensuring 64 patients per arm to complete Quality of Informed Consent part A comprehension survey. An interim analysis revealed that the survey completion rate was lower than expected, and then the target sample size was increased to 198 with expected 99 patients per group and 64 per arm to complete the Quality of Informed Consent part A questionnaire.

Study Status and Publication Plan:

The study opened enrollment in November 2013 and closed in August 2016 when the targeted sample of 198 patients was enrolled. Two manuscripts are anticipated from this trial. The first manuscript will describe the qualitative study and will detail the barriers and facilitators that were identified on semi-structured interviews of participating site research and IRB personnel. The analysis for this manuscript has been completed. The second manuscript will present the analysis of the randomized study that is detailed in this statistical analysis plan. We plan to circulate the first draft of the manuscript to the protocol team for review within 6 weeks after the analysis has been reviewed.

Survey instrument scoring:

- The Quality of Informed Consent Parts A and B will be scored as described in (Joffe et al, 2001)

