- The Rapid Estimate of Adult Literacy Revised (REALM-R, a health literacy measure) will be scored as described in (Bass et all, 2003): words “fat”, “flu”, and “pill” will not be scored.
- The New Vital Sign (a health literacy measure) will be scored as described in (Weiss et al, 2005)
- The State-Trait Anxiety Inventory (STAI) will be scores as described in its manual (Spielberger et al, 1983)

NCT02081248

- The Consent Form Satisfaction Survey will be summarized by its total score as the sum of responses to its seven Likert questions (0-4).
- The Deaconess Informed Consent Comprehension Test will be scored as described in (Miller et al, 1996). The total score ranges between 0-28.

Primary Endpoint and Data Analysis:

The primary endpoint of BMT CTB 1205 is the mean comprehension score on the Quality of Informed Consent (part A) instrument.

The primary analysis will be performed using all patients who completed the Quality of Informed Consent (Part A) and will be based on the two sample t-test or, if the t-test assumptions are violated, with Mann-Whitney test. The statistical significance will be declared if the P-values of a two-sided test <0.05 .

The following non-primary analyses will use all randomized patients with possible exclusion of clinical trials protocols with high missing data rates. Non-primary analysis will rely on linear regression models with multiple imputations to address missing data issues.

Analysis of interactions between the randomized assignment and (1) the trial protocol, (2) literacy level (REALM-R), (3) income, (4) age groups, (5) education level. The statistical significance of interactions will be declared at ALPHA 0.01 (Bonferroni adjustment for 5 tests). If the interaction test is significant then post-hoc comparisons between the ETRIC and standard consent groups will be performed for each level of a categorical variable.

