Data preparation: We will investigate functional forms of continuous predictor variables, such as "literacy level" (assessed via NVS or REALM-R) and "age" and the use of appropriate transformations of continuous predictors to make the associations with the outcome more linear and the distributions of model residuals closer to normal. We will also consider grouping continuous variables into three categories by tertiles if the linear association with the outcomes is not adequate. The categories of variables with multiple levels, such as "Education level" or "Income", will be grouped into wider categories.

The adjusted analysis of the primary endpoint will be based on the linear regression model. Potential confounding variables to include in the model are (1) the trial protocol, (2) literacy level (NVS or REALM-R, whichever is more predictive), (3) income, (4) gender, (5) age, (6) categorized race (WHITE vs OTHER). Forward stepwise variable selection will be used to find a parsimonious linear regression model with significant at ALPHA = 5% predictors.

Missing data: Since only near two thirds of all study participants are expected to complete the Quality of Informed Consent (Part A) questionnaire, we will develop an imputation model and use multiple imputations to fill-in missing values. The imputation model will use the information at baseline when the participant is enrolled into the study. Then, we will use Little and Rubin's approach (Little & Rubin, 2002) to combine the results of multiple imputations for estimating model parameters, variance covariance matrices, and P-values. To investigate the possibility of missing data which are not missing at random (NMAR), we will use tipping-point

NCT02081248

approach and find the ranges of the imputation model parameters when the inference on the effect of ETRIC consent does not change.

Dependence within data: The linear mixed models will be used to explore whether there is a need to control for clinical trial site or clinical trial site by protocol, both or neither.

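### The SAP lets whole parent protocols with undefined high missingness be dropped from its only all-randomised analyses of QuIC Part A

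*SAP*

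**What the plan says.** The SAP runs the primary QuIC Part A comparison on patients who completed that questionnaire, and repeats this under Patients to Include. Directly after defining the primary test, it says that the non-primary analyses "will use all randomized patients with possible exclusion of clinical trials protocols with high missing data rates". The next sentence ties those analyses to linear regression with multiple imputation. The interaction tests, the adjusted model, the imputation and the tipping-point analysis follow under the same heading. No threshold for *high* is given, nor who decides, when, or how an exclusion is reported.

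Elsewhere in the documents:

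- Protocol 5.1 says that patients who joined 1205 "prior to the BMT CTN 0901 and BMT CTN 1203 closures will be included in the analysis".
- Protocol 5.5: "The primary analysis will be performed using the intention-to-treat principle so that all randomized patients will be included in the analysis".
- Protocol 5.5 on missing data: "The presence of missing data in excess of 10% will be addressed by developing an imputation model". It gives no option to drop a parent trial.
- SAP, Missing data: "Since only near two thirds of all study participants are expected to complete the Quality of Informed Consent (Part A) questionnaire", imputation will be used.
- SAP, interactions: "Analysis of interactions between the randomized assignment and (1) the trial protocol" heads the list, and the Table 3 shell has a row for each of 0901, 1101, 1203 and 1301.
- SAP, Secondary Endpoints: all enrolled patients are analysed, with no exclusion option.

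**The concern.** Because the primary test is restricted to completers, the non-primary models are the only place where the SAP analyses QuIC-A on all randomised patients. They are also where the SAP examines what the missing third might do to the result. The exclusion clause allows the parent protocols with the most missing forms to be taken out of that examination. Non-completers from an excluded protocol would then appear in no QuIC-A analysis at all.

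Timing adds to this. The SAP is dated 9/17/16. Enrolment had "closed in August 2016 when the targeted sample of 198 patients was enrolled", and the synopsis records that "An interim analysis revealed that the survey completion rate was lower than expected". Completion by arm or by parent protocol is not reported, and nothing suggests that results were known. Even so, an undefined exclusion rule written at that stage leaves the analysed population to a later choice.

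**Working it through.** **The plan's own figures.** Protocol 5.2 uses a difference of 4, SD 8, two-sided 5% and 80% power. The exact t calculation gives 63.8, so 64 per arm. Dividing by the relative efficiency, 64 / 0.864 = 74.07, taken as 74 per arm or 148 in total. Allowing 25% dropout, 148 / 0.75 = 197.3, so 198. The stated 64, 148 and 198 reproduce. The exclusion clause does not touch them.

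**Expected missing forms.** The SAP synopsis expects 64 completers in each arm of 99.

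- Completers: 2 × 64 = 128.
- Missing: 198 − 128 = 70, and 70 / 198 = 35.4%.
- This is about 3.5 times the protocol's 10% trigger. That trigger therefore cannot stand in for *high*: the study as a whole already exceeds it.

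**Size of the closed parent protocols (Protocol Appendix G, approximate counts).**

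- 0901: 19 / 198 = 9.6%, leaving 179.
- 1203: 100 / 198 = 50.5%, leaving 98.
- 1101 and 1301 together: 198 − 119 = 79. Their split is not given, so they are not bounded separately.

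**Bounds on what would leave the check.** Completion by parent protocol is not reported. The only assumption is that an excluded protocol has a missing rate above the overall 35.4%.

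- 0901, minimum: 19 × 0.3535 = 6.7, so 7 forms (7 / 70 = 10%). Maximum: all 19 (19 / 70 = 27%).
- 1203, minimum: 100 × 0.3535 = 35.4, so 36 forms (36 / 70 = 51%). The arithmetic ceiling of 70 requires every other patient to complete, so it is not used.

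**Missing share left after exclusion.** The 40% and 50% rates are illustrations, not reported figures.

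| Excluded | Missing forms removed | Share still missing |
|---|---|---|
| None | 0 of 70 | 70 / 198 = 35.4% |
| 0901, minimum | 7 of 70 (10%) | 63 / 179 = 35.2% |
| 0901, maximum | 19 of 70 (27%) | 51 / 179 = 28.5% |
| 1203, minimum | 36 of 70 (51%) | 34 / 98 = 34.7% |
| 1203 at 40% missing | 40 of 70 (57%) | 30 / 98 = 30.6% |
| 1203 at 50% missing | 50 of 70 (71%) | 20 / 98 = 20.4% |

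In a tipping-point analysis, each point by which the imputed scores in one arm are shifted moves that arm's mean by its missing share. If the share is equal in both arms, that is 0.35 points with everyone included and 0.20 points in the last row. The estimate would look less sensitive to the missing forms because fewer of them are in the analysis. The smaller sample also widens the interval, so whether significance would tip sooner or later cannot be said in advance.

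**Text against text.** Protocol 5.1 includes the 0901 and 1203 enrollees; the SAP clause permits leaving them out. Protocol 5.5 prescribes imputation when missingness is high; the clause permits exclusion instead. The SAP plans a treatment-by-protocol interaction with four levels; an exclusion removes one.

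**The case against.** The best case for the SAP has five parts.

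1. Protocol 5.1 does not name which analysis it means. Completers from 0901 and 1203 would stay in the primary test, and all enrollees in the secondary-endpoint analyses. This is fair as far as it goes. But non-completers from a dropped protocol would be in no QuIC-A analysis, which is hard to square with the plain wording.
2. The intention-to-treat sentence in 5.5 concerns the primary analysis, and the completers-only primary set is a separate departure from it. This is correct. It is also why the non-primary models matter: they are all that remains of an all-randomised QuIC-A analysis.
3. The SAP does impute, and 5.5 sets no limit per parent protocol. True, but for the patients of an excluded protocol, exclusion takes the place of imputation.
4. The Missing data paragraph speaks of all study participants and does not repeat the exclusion, so its reach into the tipping-point work is partly inferred. The clause also does not say whether the missing rates are for QuIC-A or for covariates. The first point is largely answered by the sentence after the clause, which ties the same analyses to multiple imputation. The second stands as a further ambiguity in the SAP.
5. The exclusion is only possible, and the table shells list all four protocols. This stands: full inclusion may well be the default. If so, deleting the clause gives up nothing.

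It also stands that no bias or change in error rate has been shown. Randomisation was stratified by parent protocol (Protocol 5.1.2), so the arms remain comparable within whatever set is kept.

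**Conclusion.** The concern holds. The SAP contains an undefined, discretionary exclusion that would contradict protocol 5.1 if applied to 0901 or 1203. Applied to any parent protocol, it would depart from the imputation rule in protocol 5.5. Its effect is confined to the non-primary QuIC-A analyses.

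The effect would be small for 0901, with at most 27% of the missing forms leaving the check. It could be large for 1203, with at least 51% leaving and about half the patients gone. These figures rest on the approximate enrolment counts in Appendix G, on 70 expected missing forms (the two-thirds wording would give 198 / 3 = 66), and on an excluded protocol having a missing rate above the overall one. Whether the option would be used, and on which protocol, cannot be told from the documents. The point should be corrected, but it does not threaten the primary result.

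**What to change.** Delete the exclusion clause from the SAP sentence on non-primary analyses. State instead that these QuIC-A analyses use all randomised patients from 0901, 1101, 1203 and 1301, with parent protocol as a term in the imputation model. If the team wants to see results without a poorly completed protocol, present them as a labelled sensitivity analysis beside the full-sample result. Defining *high* alone would not be enough, because it would leave the conflict with protocol 5.1 and 5.5 in place.

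The cost is one SAP sentence. The downsides are wider imputation uncertainty where many forms are missing and an imprecise interaction estimate for 0901, with about 19 patients.

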5.1.2. Randomization

Patients will be randomized at a ratio of 1:1 between the two consent arms. Randomization will be stratified by center and by parent BMT CTN treatment protocol. Study ID numbers will be randomized within strata. Study personnel will be blinded to randomization assignment until a study participant agrees to participate and is assigned a study ID number.

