Age (years)			
Education Level			

 - Education Group 1 (N) - Education Group 2 (N) - Education Group 3 (N) - ... - Missing (N) 			

* P-values column will provide global interaction tests and P-values for post-hoc comparisons between the regression coefficients ETRIC and standard consent groups (Missing Data group will be excluded from calculations).

Table 4: Adjusted analysis of Quality of Informed Consent (part A) instrument

Table will report the results of a parsimonious regression model

	Regression coefficient (+/-SE)	P-value
(Model intercept)	Coef (SE)	
ETRIC	Coef (SE)	
Covariate 1		

 - Category 1 	Coef (SE)	

NCT02081248

- Category 2	Coef (SE)	
- ...		
- Reference Category	0 (-)	
Covariate 2		
- Category 1 of Covariate 2	coef (SE)	
- Category 2 of Covariate 2	coef (SE)	
- ...		
- Reference Category of Covariate 2	0 (-)	
...		

P-values column will provide global P-values and P-values of post-hoc comparisons between versus the reference category. Indicator of ETRIC will always be included in the regression model; inclusion of other variables will depend on their significance level (<0.05).

References:

1. Steven Joffe, E. Francis Cook, Paul D. Cleary, Jeffrey W. Clark, Jane C. Weeks Quality of Informed Consent: a New Measure of Understanding Among Research Subjects *Journal of the National Cancer Institute*, Vol. 93, No. 2, January 17, 2001
2. Roderick Little and Donald Rubin. Statistical Analysis of Missing Data, 2002, 2nd ed., Wiley
4. Spielberger, C. D., Gorsuch, R. L., Lushene, R., Vagg, P. R., & Jacobs, G. A. (1983). Manual for the State-Trait Anxiety Inventory. Palo Alto, CA: Consulting Psychologists Press.
7. Little R. and Rubin D, Statistical Analysis with Missing Data. 2nd ed, 2002, Wiley

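### The SAP's adjusted ETRIC analysis picks its covariates by significance on the same outcome and has no selection rule across imputations, so Table 4 is not determined by the plan and its standard error is slightly too small

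*SAP*

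**What the plan says.** The adjusted analysis is described in the SAP under Data preparation, within Primary Endpoint and Data Analysis. It is a linear regression with six candidates: parent protocol, literacy, income, gender, age and race. The selection rule is: "Forward stepwise variable selection will be used to find a parsimonious linear regression model with significant at ALPHA = 5% predictors". The literacy candidate is "NVS or REALM-R, whichever is more predictive". Functional forms are also left to the data; the same part of the SAP allows "grouping continuous variables into three categories by tertiles if the linear association with the outcomes is not adequate".

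The note under SAP Table 4 says that the ETRIC indicator always stays in, while "inclusion of other variables will depend on their significance level (<0.05").

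Protocol 5.1.2 states: "Randomization will be stratified by center and by parent BMT CTN treatment protocol". Center is not among the six candidates; the SAP leaves site to exploratory mixed models. Education is not a candidate either, although it is one of the five factors to be tested for interaction with ETRIC. That interaction list fixes literacy as REALM-R.

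The SAP has the non-primary analyses use multiple imputation, because only about two thirds of participants are expected to complete QuIC part A. Parameters, covariance matrices and P-values are then combined over imputations. The primary analysis is an unadjusted t-test or Mann-Whitney test in completers.

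Protocol 5.5 plans adjustment by GEE, with demographics, literacy and strata as examples of covariates. It adds interactions if significant but describes no selection of main effects.

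**The concern.** There are three problems.

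1. When covariates are chosen by their P-values on the outcome being modeled, the final fit treats the chosen model as if it had been known in advance. The reported standard error and P-value for ETRIC leave out the selection step.
2. Randomization was stratified by parent protocol and center. An adjusted analysis would normally carry the strata. Here one can be removed for want of significance and the other never enters the list.
3. Selection and imputation are both required, but the plan does not say in what order, or what happens when imputed data sets disagree. Two analysts following the SAP faithfully could report different covariate lists, different literacy scores and different ETRIC estimates in Table 4.

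Table 4 is the SAP's only planned table of a covariate-adjusted ETRIC effect. With about a third of outcomes missing, readers are likely to use it to judge the completers-only primary result.

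**Working it through.** **Plan's own figures.** The documents give no standard error or power for the adjusted model, so only the sample size can be reproduced. With a 4-point difference, SD 8 and two-sided 5%, the noncentral t gives 80.1% power at 64 per group and 79.5% at 63, so 64 is right. For Mann-Whitney, 64/0.864 = 74.07, which supports 74 per group or 148 in total. With dropout, 148/(1 - 0.25) = 197.3, so 198. The SAP expects 64 of 99 per arm to complete: 64/99 = 64.6%.

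**Simulation of the selection rule.** There were 4,000 data sets per scenario with no ETRIC effect, complete data, 1:1 allocation and residual SD 8. Sample sizes were 128 (64 per arm) and 198. ETRIC was forced in and the better-fitting of two correlated literacy scores was offered. Forward entry at p < 0.05 ran over protocol (4 levels), literacy, income (3 groups), gender, age and race. The comparator kept all of these, with NVS as the literacy score. Covariate distributions and the strength multiplier (0 to 1.0) are assumptions; the documents give neither.

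Ratio = mean reported SE / empirical SD of the ETRIC coefficient; 1 is correct.

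| N | Strength | Ratio, fixed | Ratio, stepwise | Difference | Type I, fixed | Type I, stepwise |
|---|---|---|---|---|---|---|
| 128 | 0 | 0.989 | 0.976 | 0.013 | 5.08% | 5.80% |
| 128 | 0.3 | 1.004 | 0.976 | 0.028 | 4.78% | 5.70% |
| 128 | 0.6 | 0.978 | 0.952 | 0.026 | 5.78% | 6.22% |
| 128 | 1.0 | 0.985 | 0.960 | 0.025 | 5.15% | 5.70% |
| 198 | 0 | 1.002 | 0.991 | 0.011 | 5.25% | 5.48% |
| 198 | 0.3 | 1.006 | 0.989 | 0.017 | 4.88% | 5.25% |
| 198 | 0.6 | 0.990 | 0.968 | 0.022 | 5.20% | 5.75% |
| 198 | 1.0 | 0.996 | 0.988 | 0.008 | 4.90% | 5.35% |

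The part due to selection is the difference between the two ratios: 0.008 to 0.028, or about 1-3%. Type I error rises by 0.2 to 0.9 points. The simulation error of each rate is sqrt(0.05 × 0.95/4000) = 0.34 points.

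**Second design.** With 128 completers, six covariates assumed to explain 25% of the variance and 10,000 trials, stepwise selection gave ratio 0.968 and type I error 5.5%. The fixed model gave 1.000 and 4.8%. Selection again accounts for about 3%.

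**Analytic check.** With 117 residual degrees of freedom the critical t is 1.980. If the SE is 3% too small, the effective cut-off is 0.97 × 1.980 = 1.921, a two-sided error of 5.7%. If it is 1% too small, 0.99 × 1.980 = 1.961 and the error is 5.2%. This agrees with the simulations.

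**Selection under imputation.** There were 200 simulated trials per scenario, each with 198 randomized, about 35% of outcomes missing completely at random and 20 imputations, with the stepwise rule applied in each imputed data set.

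| Strength | Trials with more than one selected model | Median distinct models | Literacy term (which score, or none) differs |
|---|---|---|---|
| 0.3 | 100% | 9 | 77% |
| 0.6 | 100% | 7 | 26% |
| 1.0 | 99% | 4 | 2% |

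**Omitted covariates.** In the first simulation the model with no covariates at all had ratios of 0.980 to 1.006 and type I error of 4.9-5.4%.

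**The case against.** The strongest defense is that this is a supportive analysis of a randomized comparison with the treatment term forced in. The primary test does not depend on it, and the error in the standard error is small. That stands, and it limits the point to a supportive result.

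A second defense is that the SAP pools P-values and Table 4 speaks of a single model, so selection on pooled P-values would yield one model and fits the text. This is a fair reading, but the SAP does not state it. A reader might infer that estimates from differing models cannot be combined at all. That goes too far: ETRIC is in every model, and in a linear model with randomized treatment its coefficient targets the same mean difference whichever covariates enter. What the plan leaves open is the covariate list, the literacy score and the remaining rows of Table 4.

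A reader might also infer that leaving out education makes the standard error too small. It does not. Omitting a prognostic covariate from a randomized comparison can cost precision but leaves the standard error valid, as the no-covariate results show. The education point is one of inconsistency with the interaction list.

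Nor is stepwise regression the only adjustment anywhere in the documents. Protocol 5.5 has its GEE, and the SAP has exploratory mixed models and a fallback GEE with leave-one-site-out standard errors. None of these settles which covariates enter Table 4.

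Finally, the standard-error simulations use complete data, with no site effect and no search over transformations or tertiles. That limits how exactly the 1-3% can be read. The search over functional forms could add to it.

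**Conclusion.** The concern holds for the non-primary adjusted analysis. The plan selects covariates and the literacy score on the outcome, allows one randomization stratum to drop out, does not list the other, and gives no rule for selection across imputations. The last is the more consequential gap: under the assumed strengths, imputed data sets almost always select different models.

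The effect on inference is real but small. The standard error for ETRIC is about 1-3% too small because of selection, and type I error is about 5.3-6.2%, against about 5% for a fixed model. These sizes rest on assumed covariate distributions and strengths.

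A reader might infer that the trial's main conclusion is at risk. The documents do not support that, because the primary test is unadjusted and uses none of this machinery. This is a change that should be made, not one on which the primary result depends.

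**What to change.** In the SAP, replace stepwise selection with one fixed covariate set:

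- ETRIC and parent protocol;
- a stated handling of site, for example a random intercept or a rule for pooling small sites;
- one named literacy score (REALM-R would match the interaction analysis);
- the other covariates already listed: income, gender, age and race;
- a stated decision on education, with the reason.

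Fix the functional forms and category groupings in advance. Keep all terms whatever their significance, and fit this same model in every imputed data set before pooling. Delete the choice of literacy score by predictive strength and the significance condition under Table 4. If selection is kept for exploration, state the rule across imputations and label the result exploratory.

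The cost is SAP wording and a few degrees of freedom. In the first simulation at N = 128, the true SD of the ETRIC coefficient under the fixed model was 3% larger than under stepwise selection when no covariate mattered (1.481/1.438 = 1.030). It was about equal at strength 0.3 (1.459 against 1.455) and smaller at 0.6 (1.501 against 1.514) and 1.0 (1.498 against 1.521). Terms for site and education were not simulated and would use further degrees of freedom.
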